1.0 BACKGROUND AND RATIONALE

1.1 Whipple Procedure

The procedure was originally described by Alessandro Codivilla in 1898. A.O. Whipple improved it in 1935. The Whipple procedure is the standard method for therapy of cancerous tumors, inflammation and stenosis near the head of the pancreas.

Approximately 100 patients undergo an elective Whipple procedure at Washington University Medical Center each year.

1.2 Thunderbeat™

As the pancreas is fed by many vessels, it is necessary to use lots of ligatures, clips and sutures for hemostasis after dissection. This dissection technique is very time consuming and requires numerous changes of instruments. The devices we currently have available for use in the operating suite are EnSeal and LigaSure. A new type of surgical scissors that delivers ultrasonically generated frictional heat energy and electrically generated bipolar energy simultaneously, known as the Thunderbeat™ (Olympus, Japan), is now an available alternative for dissection and hemostasis. [1-2]

Thunderbeat™ was provided FDA clearance in March 2012 for use in open, laparoscopic, and endoscopic surgery, or in any procedure in which cutting, vessel ligation (sealing and cutting), coagulation, grasping and dissection is performed.

The Thunderbeat™ device provides the first integration of both bipolar and ultrasonic energies delivered simultaneously from a single multi-functional instrument. This integration provides the surgeon the ability to rapidly cut tissue with ultrasonic energy and to create reliable vessel seals with bipolar energy without having to change devices. The current is provided by a special generator and contains a very high capacity with a low voltage. The body's proteins, such as collagen and elastin, are converted so a permanently sealed zone results. As the tissue between the branches is sealed, lateral thermic tissue damages can be limited to a minimum. Several authors have described a tendency of reduced intraoperative blood loss with bipolar energy devices. Other trials show reduced operating time when a bipolar device is utilized in several surgical procedures, such as thyroid, hepatic, urologic, hemorrhoidectomy and gynecology surgery. [3-7]

Correct dissection in the operating field is very important to avert secondary bleeding or other complications, which might cause re-operation or elevate the patients' morbidity and mortality.

The main difference between the predicate devices and the Thunderbeat™ seal and cut mode is that Thunderbeat™ uses ultrasonic and high frequency bipolar energy simultaneously to seal and cut tissue.

2.0 OBJECTIVES

2.1 Primary Objective

This is a prospective observational feasibility/QI registry trial to evaluate operative blood loss and post-operative morbidity following use of the Thunderbeat™ device during the Whipple procedure. This will be compared to patients whose Whipple procedure will be performed using conventional dissection and hemostasis techniques.

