9.0 STATISTICAL CONSIDERATIONS

9.1 Study Objectives and Endpoints

The primary objective of the study is to determine if the use of the Thunderbeat™ device provides a reduction in operative blood loss. The measurement of operative blood loss will come from the intraoperative anesthesia notes where estimated blood loss is recorded during each surgical procedure.

The secondary objectives are intraoperative and postoperative morbidity, hospital length of stay and operative time.

Primary endpoint

The primary endpoint will be the estimated operative blood loss. The estimated blood loss will be measured per the standard of care and will be documented in the operation log.

Secondary endpoints

- Operation time measured from the beginning of the surgical procedure (incision of the skin) to the end of the surgical procedure (closure of the skin).
- Anesthesia time measured from the initiation of anesthesia induction to the time of extubation
- Perioperative complications:
 - Iatrogenic injury
 - Need for conversion from laparoscopic approach to open procedure
 - Need for the use of other hemostatic devices or therapies
 - Intraoperative requirement of blood product transfusion
- Postoperative complications through 90 days from day of surgery:
 - Secondary bleeding/hematoma
 - Wound infection
 - Gastroparesis
 - Postoperative pancreatic fistula
 - Intraabdominal abscess

- Anastomotic leakage
- Re-intervention (operational)
- Postop requirement for blood product transfusion
- Hospital mortality
- Overall cost of the operation, calculated by the indirect and direct costs during the hospital stay and the costs accumulated 90 days postoperatively

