9.3 Sample Size

Appropriate sample size is calculated based on assumption of difference of 20 percent in blood loss in favor of the Thunderbeat™ device as compared with conventional techniques. This difference is considered clinically relevant based on previous similar studies [9-11]. A sample size of 60 is considered sufficient to prove this difference, if present (alpha error set at 0.05, power>80 percent).

Approximately 100 patients per year undergo a Whipple procedure at Washington University Medical Center. The estimated time frame to enroll 60 patients is approximately 18 to 24 months.

The total expected enrollment is 60 patients: 30 Thunderbeat and 30 conventional.

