9.4 Data Analysis

Data analysis for this study will be descriptive in nature. Demographic and clinical characteristics of the sample, as well as intraoperative findings and post-surgery complications will be summarized using descriptive statistics. The incidences of surgical complications and procedure-related adverse events will be calculated, and the confidence intervals will also be provided.

Patients assigned to the Thunderbeat™ group will be compared with those who had conventional techniques using χ^2 tests for categorical variables and Student's t-tests for continuous variables. For the t-tests equal variances were not be assumed, unless significant by Levene's test. Mann-Whitney *U* tests will be utilized for non-normally distributed variables. Two-tailed *P* values 0.05 will be considered statistically significant.

Multivariate analyses for intraoperative blood loss (mL), operative time (minutes), postoperative morbidity (any grades 1–5 and major grades 3–5), and hospital length of stay (days) will be performed using binary logistic regression and linear regression models to examine the relationship between intervention groups and examined outcomes and to identify potential confounders. The results of multivariate analyses will be expressed as odds ratios with corresponding 95% confidence intervals. All analyses will be performed using SPSS 20.0 statistical software (SPSS Inc.Chicago, IL).

REFERENCES

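### Section 2.1 puts morbidity in the primary objective against 9.1, and 9.4 labels no blood-loss analysis as primary and states two rules that are wrong as written

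*Combined protocol and SAP*

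**What the plan says.** **Objectives and endpoint.** Section 2.1 gives the primary objective as "to evaluate operative blood loss and post-operative morbidity following use of the" device, compared with conventional technique. Section 2.2 lists only operative time and cost as secondary. Section 9.1 differs: "The primary endpoint will be the estimated operative blood loss", and "The secondary objectives are intraoperative and postoperative morbidity, hospital length of stay and operative time".

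**Sample size.** Section 9.3 rests on blood loss only: "Appropriate sample size is calculated based on assumption of difference of 20 percent in blood loss", with alpha 0.05, power above 80 percent and 30 patients per arm. It adds that "A sample size of 60 is considered sufficient to prove this difference, if present". It gives no mean or standard deviation, and no morbidity rate.

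**Analysis.** Section 9.4 opens with "Data analysis for this study will be descriptive in nature", then sets a test threshold: two-tailed P "values 0.05 will be considered statistically significant". It compares the arms by t-test for continuous variables, or by Mann-Whitney for variables that are not normal, with no criterion for deciding that. On variances it says that "equal variances were not be assumed, unless significant by" Levene's test. It then puts blood loss in mL, operative time in minutes, length of stay in days and morbidity into linear and logistic regressions, which are also meant to find confounders. No covariates are listed. All multivariate results are to be given as odds ratios.

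**The concern.** Two sections rank the same outcome differently, and the analysis section does not say which blood-loss result carries the conclusion. The descriptive label does not remove the need for that choice, because 9.3 aims to prove a difference and 9.4 sets a significance threshold; together they invite a claim of reduced blood loss. If the unadjusted test and the regression fall on opposite sides of 0.05, the plan has no explicit rule for which one to report as the result. The choice could then be made after the data are seen.

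Two instructions in 9.4 also cannot stand as written. A linear regression of mL, minutes or days yields a difference, not an odds ratio, and an odds ratio could not express the 20 percent reduction in 9.3. The Levene clause assumes equal variances only when the test indicates that they differ.

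**Working it through.** **1. Rank of morbidity.** Section 2.1 says primary, 9.1 says secondary, and 9.3 gives no morbidity figure. Section 2.1 states no success rule. If it were read as two primary outcomes at 0.05 each:
- either one suffices: 1 - 0.95² = 0.0975 if independent (0.091 at correlation 0.5)
- both required: 0.05² = 0.0025 (0.009 at correlation 0.5), so no inflation

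**2. The plan's own figure.** N = 60 cannot be reproduced, because 9.3 gives no spread. It can be solved backwards for the CV that yields 80% power at 30 per arm (two-sided, normal approximation):
- standardized difference = (1.960 + 0.842) × √(2/30) = 0.723
- CV = 0.20 / 0.723 = 0.276

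The t-test version gives 0.272 and a one-sided version 0.312. So 9.3's power claim implies a CV of about 0.28.

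**3. Do the two EBL analyses agree?** This was simulated with 30 per arm and log-normal EBL. None of the following comes from the documents:
- Spread: CV 0.276 (implied by 9.3), 0.5 and 0.8.
- Unadjusted rule: Welch t-test, or Mann-Whitney if Shapiro-Wilk p < 0.05 in either arm.
- Regression: EBL in mL on arm plus covariates with univariate p < 0.05.
- Covariates: one or three, each correlated 0.2 or 0.4 with log EBL.
- Trials per setting: 8,000 null and 5,000 with a 20% reduction at CV 0.5 and 0.8; 2,000 at CV 0.276.

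With no true effect, at CV 0.5 and 0.8, the unadjusted rule alone rejects in 4.6-5.2% of trials and the regression alone in 4.4-5.0%. Neither is faulty by itself.

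| Covariates | Either significant, no effect: CV 0.5 / 0.8 | Disagree, true 20% reduction: CV 0.276 / 0.5 / 0.8 |
|---|---|---|
| one at 0.2 | 6.8% / 6.9% | 4.8% / 12.0% / 11.9% |
| one at 0.4 | 7.1% / 6.8% | 6.4% / 18.6% / 15.1% |
| three at 0.4 | 8.1% / 8.5% | 13.6% / 30.1% / 22.5% |

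At CV 0.276 the null either-significant rate is 6.2-7.9%. A repeat gave disagreement of about 5-11% at CV 0.276 and 14-29% at CV 0.5, so the upper figures are uncertain by a few points. A different set-up, taking the smallest p-value of Welch, Mann-Whitney and a one-covariate regression, gave 7.4-8.7% under the null.

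**4. What the largest disagreement consists of.** In the setting with three covariates at 0.4 and CV 0.5, one run showed 30.8% disagreement. Trials significant only in the unadjusted test made up 7.6%, leaving 30.8 - 7.6 = 23.2% significant only in the regression. Three independent covariates at 0.4 explain 3 × 0.4² = 48% of the variance of log EBL, so this is mostly the regression gaining power on a true effect.

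**5. Smaller choices.** At CV 0.5-0.8, Welch and Mann-Whitney disagree in 2.9-3.9% of null trials and 10-12% of trials with the 20% effect, so the missing normality criterion has some weight. Pooled and Welch t-tests differ in only 0.07-0.14% of null trials, so the reversed Levene rule has little effect at 30:30.

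**The case against.** The strongest defence is that the plan answers most of this itself. Section 9.1 names one primary endpoint and lists morbidity as secondary, so 2.1 is a mismatch in an introductory section. Section 9.4 uses the t-test or Mann-Whitney test to compare the arms and gives the regressions a broader, exploratory purpose, so the natural reading is that the unadjusted test is the comparison. Both arguments have weight and limit the consequence. They do not remove the contradiction in 2.1, supply the missing label or normality criterion, or repair the two wrong rules.

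A reader might infer more than the documents support:
- **That the trial has two primary outcomes and a 9.75% error rate.** Section 2.1 states no either-or rule, and 9.1 points the other way.
- **That up to 30% of trials would reach a wrong verdict.** Disagreement is not error. The figure needs a CV well above the one that 9.3 implies, together with strong covariates. The lower power at that CV is a sample-size matter, separate from this point.
- **That the plan will report whichever analysis is significant.** It does not say so; 6-9% is the rate if either were allowed to decide.
- **That EBL has three competing sources.** Sections 5.3 and 9.1 both name the anesthesia notes, and the nursing sentence in 5.3 describes how volume is measured. Only the operation log in 9.1 is stray wording.

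The Shapiro-Wilk rule and the covariate screen are modelling assumptions; 9.4 states neither.

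**Conclusion.** The point holds as one of consistency and missing labels, with moderate consequences. The textual parts are certain: 2.1 conflicts with 9.1, 9.4 designates no primary EBL analysis, and its odds-ratio and Levene rules are wrong as written. The size is less certain, because the documents give neither the spread of EBL nor any covariate strength. If either analysis may decide, false positives are about 6-9% rather than 5%. With a true 20% reduction, the analyses disagree in about 5-14% of trials at a CV of about 0.28 and in 12-30% at CV 0.5; where covariates are strong, most of this is added power in the regression. The Levene error is negligible in effect with equal arms of 30.

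**What to change.** - **2.1 and 2.2:** move post-operative morbidity to 2.2 so that it agrees with 9.1. Hospital stay, secondary in 9.1 but absent from 2.2, can be added in the same edit.
- **9.4, primary analysis:** name one comparison of EBL by randomized arm, fixed in advance. The simplest is the two-sided t-test already listed, in Welch form, with no Levene or normality pre-test. Report the mean difference in mL with its 95% CI, and also as a percent of the control mean. Section 9.3 does not say whether its 20 percent refers to means, so the plan should state this. In the simulations at CV 0.5 and 0.8 a fixed Welch test rejected in 4.3-5.0% of null trials; the simulated coverage of its interval was 95.3-95.4%.
- **9.4, other analyses:** label Mann-Whitney and the regressions as sensitivity or exploratory, and limit the descriptive sentence to endpoints other than EBL.
- **9.4, reporting:** give linear-model results as differences or ratios, and keep odds ratios for the logistic models.

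The cost is wording; sample size, data and software are unchanged. The regressions lose confirmatory status. If EBL is skewed, Welch has slightly less power for a 20% reduction than Mann-Whitney (39-41% against 40-43% at CV 0.5; 18-19% against 21% at CV 0.8). If strong covariates exist, the unadjusted test also gives up power that a regression would have (40-55% at CV 0.5 and 19-25% at CV 0.8). A primary model adjusted for covariates named in advance is an acceptable alternative, provided that those covariates are recorded.

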2.2 Secondary Objectives

1. To determine the operative time of the Whipple procedure when performed using the Thunderbeat™ device. This will be compared to patients whose Whipple procedure will be performed using conventional dissection and hemostasis techniques. Will this device reduce the amount of time spent in the operating room for both the patient and the surgeon?
2. To determine the cost of using the Thunderbeat™ device during the Whipple procedure. This will be compared to patients whose Whipple procedure will be performed using conventional dissection and hemostasis techniques. Will the use of this device be fiscally feasible?

3.0 PATIENTSELECTION

3.1 Inclusion Criteria

1. Scheduled to undergo an elective open or laparoscopic Whipple procedure
2. At least 18 years of age.
3. Karnofsky performance status \geq 80% (see Appendix A).
4. Able to understand and willing to sign a written informed consent document.

3.2 Exclusion Criteria

1. Pregnant or breastfeeding.
2. Surgeon's opinion at the time of dissection that the subject's well being (e.g. bleeding or other independent acute health problems) would be compromised.

3.3 Inclusion of Women and Minorities

Both men and women and members of all races and ethnic groups are eligible for this trial.

4.0 REGISTRATION PROCEDURES

Patients must not start any protocol intervention prior to registration through the Siteman Cancer Center.

The following steps must be taken before registering patients to this study:

1. Confirmation of patient eligibility
2. Registration of patient in the Siteman Cancer Center database
3. Assignment of unique patient number (UPN)

Once the patient has been entered in the Siteman Cancer Center database, the WUSM coordinator will forward verification of enrollment and the UPN via email.

4.1 Confirmation of Patient Eligibility

The following information is required to confirm patient eligibility prior to registering patient:

1. Registering MD's name
2. Patient's race, sex, and DOB
3. Three letters (or two letters and a dash) for the patient's initials

4. Copy of signed consent form
5. Planned date of enrollment
6. Completed eligibility checklist, signed and dated by a member of the study team
7. Copy of appropriate source documentation confirming patient eligibility

4.2 Patient Registration in the Siteman Cancer Center Database

All patients must be registered through the Siteman Cancer Center database.

4.3 Assignment of UPN

Each patient will be identified with a unique patient number (UPN) for this study. Patients will also be identified by first, middle, and last initials. If the patient has no middle initial, a dash will be used on the case report forms (CRFs). All data will be recorded with this identification number on the appropriate CRFs.

5.0 TREATMENT PLAN

5.1 Preoperative Evaluation

Eligible patients will have standard evaluations, procedures, and laboratory testing as determined necessary by their surgeon preoperatively.

5.2 Randomization

Sixty patients will be recruited according to the sample size calculation. Randomization will be performed by a Research Patient Coordinator and the patient assigned to the Thunderbeat™ group or the conventional group in a 1:1 ratio. Randomization will only occur after the patient has signed the informed consent and will be documented in the case report file as well as communicated to the treating surgeon.

Thunderbeat™ group (n=30)

In the Thunderbeat™ group, dissection and hemostasis of vessels will be performed using the Thunderbeat™ device (Olympus, Japan).

Control group (n=30)

In the conventional group, scissors, ligatures, clips and sutures will be used for dissection and hemostasis as necessary.

Minimizing treatment bias

A standardized operation technique will be used in both groups. The same Thunderbeat™ device will be used throughout the length of the study. The participating surgeons will have had experience performing at least 100 Whipple procedures to guarantee comparable treatment of patients.

Minimizing measurement bias

The patients will be blinded to the assigned operating technique. Surgeon's blinding will not be possible due to the different techniques used during the operation.

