5.3 Operative Procedure

The surgical procedure will be conducted as planned. The surgeon will follow the subject's assigned group assignment (Thunderbeat™ or conventional) unless determined to be potentially

detrimental to the optimal care of the patient. At that point, all techniques for dissection and hemostasis may be utilized as the surgeon deems necessary.

At least 5 of the procedures will be videotaped for future use to produce educational and training materials. No identifying information will be contained in the video.

The measurement of estimated blood loss (EBL) will come from the intraoperative anesthesia notes where (EBL) is recorded during each surgical procedure in Allscripts and Clindesk. The estimate of operative blood loss is measured by volume in the suction canisters and pads and is historically documented by the operative nursing staff during the operation.

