5.6 Criteria for Removal from Study

If at any time the constraints of this protocol are considered to be detrimental to the patient's health (e.g. bleeding or other acute health problem) and/or the patient no longer wishes to proceed with the protocol intervention, the patient should be removed from the study and the reason(s) for discontinuation documented in the case report forms.

Otherwise, the patient will receive the intervention and be followed as described.

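### Patients who bleed at dissection can be dropped after allocation by a surgeon who knows the arm, and no analysis rule keeps them in the blood-loss comparison

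*Combined protocol and SAP*

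**What the plan says.** Section 5.2 gives allocation a lower time limit only: "Randomization will only occur after the patient has signed the informed consent". The assignment is then "communicated to the treating surgeon", and "Surgeon's blinding will not be possible due to the different techniques used during the operation".

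Section 3.2 lists as its second exclusion criterion: "Surgeon's opinion at the time of dissection that the subject's well being (e.g. bleeding or other independent acute health problems) would be compromised". Section 4.0, by contrast, puts confirmation of eligibility first under "The following steps must be taken before registering patients to this study", and allows no protocol intervention before registration.

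Two further sections deal with the same kind of event:

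- Section 5.3 lets the surgeon leave the assigned technique when it may harm the patient's care: "At that point, all techniques for dissection and hemostasis may be utilized as the surgeon deems necessary". It does not say whether the patient stays in the data.
- Section 5.6 covers protocol constraints judged detrimental to health, again with bleeding as an example, and says "the patient should be removed from the study and the reason(s) for discontinuation documented in the case report forms".

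Section 9.1 makes estimated operative blood loss the primary endpoint. Section 9.4 names no intention-to-treat or other analysis population. It describes the Thunderbeat side by assignment and the conventional side by the technique the patients had. Section 9.3 has no allowance or replacement rule for patients lost after allocation.

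**The concern.** An eligibility criterion that can only be judged during dissection cannot be cleared before registration. Dissection is also the randomized intervention, so the judgement comes after allocation and is made by the one person who must know the arm. Its leading example, bleeding, is what the primary endpoint measures.

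If such patients are declared ineligible or removed, the upper tail of blood loss is cut. If the threshold for doing so differs between arms, even without intent, the cut is uneven and the difference in blood loss is biased. Randomization no longer protects the comparison, and with 30 per arm a few patients are enough to matter.

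**Working it through.** **1. The rules side by side, for a randomized patient who bleeds at dissection**

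| Section | Consequence as written |
|---|---|
| 3.2, exclusion 2 | Ineligible |
| 4.0 | Eligibility already confirmed before registration |
| 5.3 | Any technique allowed; status in the data not stated |
| 5.6 | Removed from the study, reason recorded |
| 9.1 | Need for other hemostatic devices or therapies is a secondary endpoint, which presumes the patient is still observed |
| 9.4 | No rule on who is analysed |

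These cannot all apply. Section 5.6 goes on to say that patients not removed are followed as described, so the natural reading is that removed patients are not.

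**2. The plan's own figure**

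Section 9.3 gives 60 patients for a 20% difference, alpha 0.05 and power above 80%. It states no mean, SD or coefficient of variation (CV), so the figure cannot be reproduced. It can be back-solved, two-sided as in section 9.4:

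- d = (1.960 + 0.842) × √(2/30) = 0.723
- CV = 0.20 / 0.723 = 0.276

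The stated power therefore needs a CV of about 0.276 or less. That is an implied value and not a documented one, so the illustration also uses assumed CVs of 0.5 and 0.8.

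**3. Worst-case illustration of selective removal**

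Set-up: 20,000 simulated trials per setting, lognormal blood loss, the same distribution in both arms (no device effect), 30 per arm. The k highest values are removed from the Thunderbeat arm only. The remaining patients are compared with the unequal-variance t-test at two-sided 5%. Each cell shows the ratio of mean blood loss (true value 1) and the false-positive rate.

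| k removed | CV 0.276 | CV 0.5 | CV 0.8 |
|---|---|---|---|
| 1 | 0.976; 7.2% | 0.951; 6.9% | 0.914; 7.0% |
| 2 | 0.958; 10.6% | 0.916; 11.7% | 0.853; 12.6% |
| 3 | 0.941; 15.9% | 0.886; 17.9% | 0.812; 18.7% |

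For k = 2 the spurious reduction is 1 − 0.958 = 4.2% at CV 0.276 and 1 − 0.916 = 8.4% at CV 0.5. The false positives fall almost wholly on one side: 9.8% and 10.9% of trials wrongly favour Thunderbeat, against a nominal 2.5%.

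The false-positive rates are for the t-test. Section 9.4 would use the Mann-Whitney test for non-normal data, and its rates would differ. The shift in mean blood loss does not depend on the test.

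**The case against.** **The exclusion may be meant narrowly.** Its reference to independent health problems can be read as limiting it to events unrelated to technique. That reading is possible, but bleeding is the first example given, and section 5.6 repeats bleeding without the word independent. The text does not secure the narrow reading.

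**Section 5.3 may be the operative rule.** If bleeding simply leads to a change of technique and the patient stays in, nothing is lost. That would be adequate if section 5.6 did not say the opposite and section 9.4 settled the analysis. Neither condition holds.

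**The simulation is one-sided.** This stands. It shows what the rules permit and does not forecast what will happen. With no true effect, equal removal from both arms would not bias the difference.

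**Stronger readings that the documents do not support**

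- *Allocation takes place weeks before surgery.* A reader might infer this from the 60-day window in Appendix B. That window is for screening. Randomization has no row in the schedule, so a long gap is possible but not planned.
- *Abandoned operations will cut power from 80% to about 70%.* This needs a loss rate of up to 20% and a known SD. The documents mention no abandoned Whipple procedures and give neither figure, so no power loss is claimed here.
- *Allocating in theatre, once exclusion 2 is cleared, would solve the problem.* The criterion is judged during dissection, which is the randomized step, so it cannot be cleared beforehand. Blood lost before allocation would also be common to both arms: if that were 10% of the total (assumed), a 20% effect on the rest becomes 0.20 × 0.90 = 18% of the whole.

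**Conclusion.** The point holds as a conflict between eligibility, removal and analysis rules. It follows from the text that a randomized patient can be excluded or removed for bleeding by a surgeon who knows the arm, and that no stated rule keeps that patient in the primary comparison. It does not follow that this will happen, or that it will differ by arm.

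If the two heaviest bleeders were lost from one arm only, mean blood loss would appear 4–8% lower with no true effect, and about 11% of trials would be falsely significant. This assumes lognormal blood loss, a CV of 0.276 to 0.5 and the t-test. Against a 20% target effect, that is large enough to correct before the analysis and cheap to prevent.

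**What to change.** 1. Reconcile sections 3.2, 4.0, 5.3 and 5.6. Eligibility should be complete before allocation. An event arising at dissection after allocation should be recorded as a departure from the assigned technique, and not as ineligibility or removal from the data. This concerns data handling only; the surgeon's discretion over care is unchanged.
2. In section 9.4, state that all randomized patients who have an operation are analysed for blood loss in the arm to which they were assigned, and describe both arms by assignment.
3. Report departures from the assigned technique and abandoned procedures by arm, with reasons.

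Allocation closer to the operation, for example on the day of surgery, is optional and does not replace step 2.

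The cost is protocol wording. Blood loss is already recorded for every operation, and use of other hemostatic devices is already an endpoint. The small downside is that crossovers dilute the contrast. If 5% of the Thunderbeat arm gained no benefit at all (assumed), a 20% effect would appear as 0.20 × 0.95 = 19%.
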